Aim#1: Determine the relationship between AAA growth rate and VV density. Approach: prospective CEUS imaging of a cohort of patients with AAA 4-5.4cm in diameter at 6 month intervals for 18 months. Hypothesis: VV density on CEUS is increased in AAA at risk for growth.

Aim#2: To correlate CEUS findings with serum biomarkers. Approach: longitudinally measure AAA specific serum biomarkers with every CEUS. Hypothesis: Levels of pro-inflammatory serum biomarkers correlate with VV density and are more elevated in unstable AAA.

APPROACH

The study protocol was approved by the Institutional Review Board (IRB) of the University of Pittsburgh. The study was funded by the AGS GEMSTAR award from the Society of Vascular Surgery (SVS) foundation in addition to the National Institute of Health (NIH) through a R03 grant.

Study Design

The objective of this study was to non-invasively study the metabolic processes within the aortic wall that are thought to explain aortic growth. This was a single center prospective evaluation of patients with an AAA diameter of at least 4.0 cm. enrolled between December

2011 and December 2016, in the outpatient vascular clinic. Patients were followed up until October 2019.

Aneurysm diameter size was determined on duplex ultrasound. Patients were excluded if they had contraindications to the administration of Definity contrast, such as pulmonary hypertension, unstable cardiopulmonary conditions, known right-to-left cardiac shunting and pregnancy. Patients underwent CEUS and serum PIB testing at enrollment and every 6 months up for 18 months or until eventual repair. PIB testing was also done one year after AAA repair..

CEUS imaging protocol

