Blood samples were withdrawn from patients at each visit and one year following AAA repair. Blood was drawn in the Vascular Surgery clinic by the research staff. Blood samples were banked and used for the measurement of biomarkers. This is the list of plasma inflammatory biomarkers that were tested: Osteoprotegerin (OPGN), Galectin 3, Cystatin C, Neutrophil gelatinase-associated lipocalin (NGAL), Uromodulin (UMOD), C-reactive protein (CRP), Macrophage migration inhibitory factor (MIF), Intercellular adhesion molecule (ICAM1), Interferon γ (IFN- γ), Interleukin 10 (IL10), Interleukin 6 (IL6), Interleukin 8 (IL8), Tumor necrosis factor- α (TNF- α), Serum amyloid A (SAA), Vascular cell-adhesion molecule (VCAM1).

Statistical analysis plan: Sample size: No previous literature has reported the mean and standard deviation of AAA VV density measured in vivo by CEUS. Statistical analysis: Data will be summarized as mean and SD for continuous variables after testing for normality.

Categorical data will be summarized with frequency and percentage. Correlation coefficients will be determined for the correlation of VV and microbubble density measured by CEUS, as well as serum biomarkers with AAA growth. We will use linear regression to test the significance of such higher VV and microbubble density by CEUS as predictor of AAA growth (Aim1). We will include serum biomarkers in the modeling process. Adjustment for any

demographics differences will be also attempted including age, gender and race. A p-value <0.05 will determine significance.

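### Adjustment is planned for demographics only, so biomarker associations that the plan reads as aortic-wall biology are open to confounding, for example by smoking or statin use

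*Combined protocol and SAP*

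**What the plan says.** The Statistical analysis plan has three analysis elements:

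- Correlations: "Correlation coefficients will be determined for the correlation of VV and microbubble density measured by CEUS, as well as serum biomarkers with AAA growth". No covariate is named.
- The Aim 1 regression, which takes VV and microbubble density as predictor and aneurysm growth as outcome. The plan adds "We will include serum biomarkers in the modeling process", without saying how.
- Adjustment for "demographics differences will be also attempted including age, gender and race". This is described as attempted, not as fixed in advance.

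Under Study Design, eligibility rests on aneurysm size ("This was a single center prospective evaluation of patients with an AAA diameter of at least 4.0 cm") and on contrast safety: "Patients were excluded if they had contraindications to the administration of Definity contrast, such as pulmonary hypertension, unstable cardiopulmonary conditions". Blood is taken at enrollment and every 6 months to 18 months or repair, and again one year after repair. Under Biomarker testing, "Blood samples were banked and used for the measurement of biomarkers", with no rule for a visit that falls during acute illness. The panel has 15 markers. They include CRP, IL6, IL8, TNF-alpha and SAA, and also cystatin C, NGAL and uromodulin.

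Aim 2 describes the serum markers as specific to the aneurysm and expects them to be higher in unstable disease. The section on anticipated findings expects biomarkers that predict growth and that will support a larger trial.

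**The concern.** The panel consists largely of systemic markers, and the background section itself describes the process as systemic inflammation. Such markers can plausibly respond to exposures outside the aortic wall. If an exposure is linked both to a marker and to growth, the two will correlate even when the marker says nothing about the wall. Current smoking and statin use are the obvious candidates. Neither is a demographic variable, so neither falls within the stated adjustment, even though that list is open-ended.

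What is at stake is interpretation. A marker that merely tracks smoking could be reported as evidence of aneurysm instability and carried into a larger trial on that basis. Confounding in the opposite direction could hide a real association. Baseline aneurysm diameter is not named as a covariate either, which is part of the same gap.

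**Working it through.** The plan gives no sample size, effect size, standard deviation or power, so there is no figure of its own to reproduce. The check has two parts.

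**1. Reading.** Smoking, statins, anti-inflammatory drugs, acute illness and kidney function were looked for in each place where they might be controlled:

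| Place | What is stated |
|---|---|
| Eligibility (Study Design) | Aneurysm size; contrast contraindications |
| Sampling (Biomarker testing) | Blood at each visit; no deferral rule |
| Controls (CEUS imaging protocol) | Matched; matching factors not given |
| Correlations (Statistical analysis plan) | No covariates |
| Regression (Statistical analysis plan) | Demographics attempted; biomarkers included |

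None of these factors appears anywhere in the available text.

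**2. Illustration of size.** Every input here is an assumption: one omitted factor, its correlation a with the marker and b with the outcome, the number of patients n, and a two-sided test (the plan gives 0.05 without sidedness).

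With true partial correlation ρ, the unadjusted correlation is

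r = ab + ρ√[(1 − a²)(1 − b²)].

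By Fisher's z, let δ = √(n − 3) × ½ ln[(1 + r)/(1 − r)]. The chance of p<0.05 is Φ(δ − 1.96) + Φ(−δ − 1.96).

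*No true association (ρ = 0, a = b).* Then r = a². For a = 0.3 and n = 100: r = 0.09, ½ ln(1.09/0.91) = 0.0902, and δ = 9.849 × 0.0902 = 0.889. The probability is Φ(−1.071) + Φ(−2.849) = 0.142 + 0.002 = 0.144.

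| a = b | Spurious r | n = 50 | n = 100 |
|---|---|---|---|
| 0.2 | 0.04 | 0.059 | 0.068 |
| 0.3 | 0.09 | 0.095 | 0.144 |
| 0.4 | 0.16 | 0.198 | 0.356 |

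The nominal rate is 0.05. These are rates for a single test.

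*Masking (ρ = 0.20, links of opposite sign).* At a = 0.3, b = −0.3: r = −0.09 + 0.20 × 0.91 = 0.092. At a = 0.4, b = −0.4: r = −0.16 + 0.20 × 0.84 = 0.008.

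*A factor unrelated to the outcome (b = 0), such as a passing infection.* The product ab is zero, so nothing spurious arises. With ρ = 0.20 and a = 0.4, r = 0.20 × √0.84 = 0.183. The effect is some loss of signal.

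*Effect of the remedy.* The partial correlation (r − ab)/√[(1 − a²)(1 − b²)] equals ρ. Including a correctly measured factor therefore restores the nominal rate when ρ = 0. A factor poorly recorded in the chart would remove only part of the bias.

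**The case against.** Several points on the other side have force.

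- **VV density and growth.** A reader might infer that the Aim 1 regression is as exposed as the biomarker analyses. The documents do not support that. They give no reason why smoking, drugs or infection should shift a background-subtracted wall intensity normalised to the lumen. Serum biomarkers also enter the modelling and may absorb some systemic inflammation. This stands, and the concern is weaker there. Biomarkers cannot adjust for themselves, however, so their own associations gain no such protection. The biomarker–VV association is confounded only if the omitted factor is linked to VV as well, which is likewise an assumption.
- **Acute illness.** A reader might infer that infections at sampling would create associations. If the illness is unrelated to growth, it adds noise instead, as shown above.
- **Size.** The documents give neither the number of patients nor any confounder strength. At a = 0.2 the excess is almost nothing. This stands.
- **Prediction.** A marker that tracks smoking can still predict growth. That is true, but the plan goes beyond prediction: it reads the markers as aneurysm biology and already attempts some adjustment.
- **Timing.** Enrollment (December 2011 to December 2016) and follow-up (to October 2019) are described in the past tense. Covariates added now may be post hoc, and some chart data may be missing. This limits the fix without removing the gap.

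**Conclusion.** The concern holds for the biomarker associations. The stated adjustment is confined to demographics, the correlations carry no covariates, and the results are to be read as specific to the aortic wall. Confounding by factors linked to both variables is uncontrolled. Whether it occurs, and in which direction, cannot be established from the documents. That smoking and statin use act as such factors here is itself an assumption.

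On the assumed values, the false-positive rate per test runs from close to nominal (6% to 7%) at links of 0.2 up to 20% to 36% at links of 0.4, for 50 to 100 patients. Only moderate or stronger links matter materially. It would go too far to conclude that background treatment has biased the results, or that the VV–growth analysis is invalid. The documents support neither. The repair is a modest, worthwhile improvement.

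**What to change.** 1. Keep age, gender and race. Abstract current smoking and statin use from the clinic record, at least at enrollment, and add both, together with baseline aneurysm diameter, to the adjusted growth and biomarker models.
2. Report these models beside those the plan already states, and label them post hoc if the data have been seen.
3. As a sensitivity analysis, repeat the biomarker analyses without samples charted as drawn during acute illness or on corticosteroids. The purpose is to reduce noise.
4. In the analyses of cystatin C, NGAL and uromodulin, adjust for creatinine where it is charted, and report how much is missing.
5. If the records cannot be retrieved, state that the associations are not adjusted for these factors and do not present them as specific to the aneurysm.

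The cost is chart abstraction, a few more model terms in a study whose size is not stated, and some missing chart data. No extra test and no change to patient care is needed.

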Patients were positioned on their back in the non-fasting state. An intravenous line was placed by the research staff at the time of the office visit. The abdominal aorta was imaged initially without contrast administration. Following non-contrast duplex imaging, CEUS was performed via intravenous administration of the ultrasound contrast agent, Definity® (Lantheus). 1ml of the contrast agent was diluted in 9ml of normal saline to achieve a concentration of approximately 10 microliters/kg. For each injection sequence, 0.5 mL contrast was injected over 2-3 sec during simultaneous burst replenishment real time imaging. Two injection sequences were typically performed. Each CEUS evaluation took approximately 20-30 minute to complete. Patient's heart rate, blood pressure and breathing were monitored during the examination and afterwards in the waiting area. The total monitoring time ranged between 30-90 minutes. Microbubble replenishment was analyzed using ImageJ (NIH) via manually drawn regions of the aortic wall and intraluminal thrombus (ILT) (Figure 1).

Ultrasound evaluation was performed using the GE US system (GE Healthcare, Chicago, IL, USA) with the standard curved array abdominal transducer. The contrast settings on the ultrasound system were set to a low mechanical index of 0.07 and a dynamic range of 50 with the focal zone placed underneath the posterior aortic wall.

Microbubble uptake was determined by the ultrasound technologist and the location was recorded on a study sheet. Uptake was then separately recorded by two of the investigators (RC, PC). Care was taken to correlate with color flow duplex ultrasound to avoid lumbar and mesenteric vessels as well as artifact. The visualization of the microbubbles within the

abdominal aortic aneurysm wall was defined as contrast uptake. This was determined by consensus agreement between the ultrasound sonographer and two investigators (The PI, RC and PC) for every single patient.

Uptake was quantified via video intensity analysis in a region of interest in the aortic adventitia. Background-subtracted peak video intensity, which has been shown to correlate with VV density, was derived and normalized to peak intensity in the lumen (Figure 2).⁹

Aneurysm growth, rupture and repair were recorded during the follow up period. Matched controls with no aneurysm disease underwent one-time CEUS and PIB testing using biomarker panels (Meso scale discovery) and Bioplex 100 analyzer (Bio-rad).

Biomarker testing

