Anticipated findings and alternative approaches: We anticipate that this clinical research study will identify biomarker and CEUS differences in AAA adventitial VV density based on age, gender and AAA stability or growth. Our findings will support a larger clinical trial and future investigations of treatment paradigms of AAA based on biologic risk of growth or rupture instead of absolute diameter. If CEUS and biomarker differences are not detected during the study period in otherwise stable AAA, longer follow up with repeated imaging and biomarker testing at 6month intervals will be sought. If our hypothesis is not confirmed (i.e. differences in AAA wall neovascularization do not exist), imaging of AAA wall inflammation will be considered when available to human subjects using microbubbles targeted to either activated leucocytes or endothelial cell adhesion molecules that are upregulated in inflammation and mediate leukocyte recruitment and adhesion. If CEUS is not accurate given the depth of penetration of ultrasound, alternative imaging modalities such as IVUS or FDG-PET CT scanning will be explored. We anticipate that our results will identify active angiogenesis and ischemia of the AAA wall and biomarker predictors of growth, which may improve real time monitoring of AAA progression and response to systemic or targeted microbubble anti-angiogenesis therapies.

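### Does the option of longer follow-up after a null finding let Aim 1 be tested twice at 0.05, and does the plan treat a null as proof of absence?

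*Combined protocol and SAP*

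**What the plan says.** All references are to the combined protocol and SAP.

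- **Statistical analysis plan.** The Aim 1 analysis reads: "We will use linear regression to test the significance of such higher VV and microbubble density by CEUS as predictor of AAA growth". The decision rule is: "A p-value <0.05 will determine significance". No analysis date, data cut-off or growth horizon is given. The sample-size entry says only "No previous literature has reported the mean and standard deviation of AAA VV density measured in vivo by CEUS"; it gives no n, detectable effect or power.
- **Aim#1 and Study Design.** CEUS is scheduled every 6 months for 18 months. Enrolment ran from December 2011 to December 2016, and follow-up ended in October 2019.
- **CEUS imaging protocol.** "Aneurysm growth, rupture and repair were recorded during the follow up period".
- **Anticipated findings and alternative approaches.** The contingency for a null finding in stable aneurysms opens "If CEUS and biomarker differences are not detected during the study period in otherwise stable AAA, longer follow up", and the action in full is "longer follow up with repeated imaging and biomarker testing at 6month intervals will be sought". A further sentence begins "If our hypothesis is not confirmed (i.e. differences in AAA wall neovascularization do not exist" and goes on to say that targeted-microbubble imaging would be considered. The section also states "Our findings will support a larger clinical trial".

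**The concern.** There are two separate worries.

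**Repeat testing.** A 5% error rate requires that the decision to test does not depend on an earlier result. Here the decision to continue depends on not having found something, no limit is put on the extension, and the regression is not tied to a time point. An analyst could test growth at 18 months, find nothing, collect more data and test again at 0.05. A significant result reached that way would carry more than a 5% false-positive risk, and it could then be used to support a larger trial.

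**Reading a null as absence.** The parenthesis treats a hypothesis that was not confirmed as one shown to be false. With no sample size or detectable effect stated, a non-significant result cannot show that. The sentence before it treats non-detection as a reason to keep looking, so the two seem to pull in different directions. A useful association might be dismissed because the study was too small to see it.

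**Working it through.** The plan states no overall error rate, n or power, so there is no figure of its own to reproduce. A single test at 0.05 has error 5.0% by definition.

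**1. Size of the error if one re-test were made**

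Inputs: alpha 0.05 (Statistical analysis plan; two-sided assumed) and first look at 18 months (Aim#1). The second look and the correlation between looks are assumptions.

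Formula: error = 1 − P(|Z1| < 1.96 and |Z2| < 1.96), with Z1 and Z2 bivariate normal with correlation ρ. If information is assumed proportional to time, ρ = √(18/T) for a second look at T months.

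| Second look | ρ | Two-sided error |
|---|---|---|
| ρ assumed directly | 0.99 | 5.66% |
| ρ assumed directly | 0.95 | 6.46% |
| 24 months | √(18/24) = 0.866 | 7.34% |
| 30 months | √(18/30) = 0.775 | 7.96% |
| 34 months | √(18/34) = 0.728 | 8.21% |
| 36 months | √(18/36) = 0.707 | 8.31% |

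The 34 months is the span from last enrolment, December 2016, to October 2019. For the earliest enrolment, December 2011, the span is 94 months.

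A simulation that regressed each patient's growth slope on a baseline predictor gave 7.3% to 8.2% for a second look at 24 months and 8.0% to 8.9% at 36 months. It assumed n = 50, between-patient slope SD of 1 to 2 mm/year and measurement SD of 2 to 3 mm. The direction is certain whenever ρ is below 1. The size depends on quantities the documents do not give.

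**2. Does the text lead to a re-test?**

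- *Trigger.* It concerns CEUS and biomarker differences in aneurysms that are otherwise stable. It names neither the regression of growth on vasa vasorum density nor its p-value. A cohort with too little growth to study fits the words at least as well as a non-significant Aim 1 test.
- *Action.* It is further imaging and blood testing. No second analysis is written.
- *Location.* The sentence is outside the Statistical analysis plan, among next-step ideas such as targeted microbubbles, IVUS and FDG-PET CT.
- *October 2019.* The extension would consist of repeated CEUS and biomarker testing. Study Design reports both on a schedule to 18 months (with a biomarker test one year after repair) and reports follow-up to October 2019 separately. Nothing identifies that follow-up as the extension, so the 8.21% row describes a second look that the documents do not contain.

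**3. What a null could show**

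Formula: 95% CI for a correlation = tanh(atanh(r) ± 1.96/√(n − 3)). Every n is assumed.

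| Observed r | n | 95% CI |
|---|---|---|
| 0 | 30 | −0.36 to 0.36 |
| 0 | 50 | −0.28 to 0.28 |
| 0 | 100 | −0.20 to 0.20 |
| 0.1 | 50 | −0.18 to 0.37 |

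A null at these sizes would leave moderate associations open. But the plan nowhere says that a null will be reported as absence. The stated consequence is only that a different imaging target would be considered.

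**The case for a change.** The strongest case for a change is that the plan makes continued data collection depend on the result and leaves the test unprotected. It does not define the study period, two growth horizons are available, and neither is assigned to the regression. The inflation is real for any imperfect correlation. The section links the expected differences to aneurysm stability or growth, which is Aim 1's subject. Calling the work exploratory does not fully answer this, because the plan sets a significance rule for a stated hypothesis. Naming one horizon and softening one phrase would need no new data.

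Several parts of this stand. The growth horizon is not stated, the arithmetic is correct, and the parenthesis claims more than a non-significant test can support.

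The step from there to a faulty analysis does not stand. That the plan fails to rule out a second test could be said of most short plans. The study period also has a natural reading: Aim#1 and Study Design both give 18 months, and the contingency repeats their 6-month interval. The two sentences on null findings can be read as separate contingencies, one for too little seen so far and one for a hypothesis that has failed, so they need not conflict.

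**Conclusion.** No change to the plan is needed. The error of about 6.5% to 8.3% arises only if Aim 1 is tested, found negative and tested once more at an unadjusted 0.05, with correlations of 0.95 to 0.71 between the two statistics. The plan describes no such sequence, and the documents do not show that it happened. With one analysis the error is 5.0%.

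Two small points are left. The first is the unstated growth horizon for the Aim 1 regression. This is missing detail that an analyst would ordinarily settle by choosing one horizon without regard to the result and saying which was used. The second is the phrase equating non-confirmation with absence, a slip of wording with no analytical consequence in the plan; giving the estimate with its confidence interval and n in the report would deal with it. The study presents itself as groundwork for a larger trial, and a confirmatory claim resting on a second look is not part of what it proposes.
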